2.1. Evaluation of preclinical testing

[figure not shown]
IGT systems Best Status: Final	Clinical Investigation Plan Observational clinical study with Surgical Navigation to plan, position and check instrument placement for spine surgery interventions	XCY607-130099 2016 Sep 16 Revision: 6.0 Page 19 of 46
--	---	--

[figure not shown]
IGT systems Best Status: Final	Clinical Investigation Plan Observational clinical study with Surgical Navigation to plan, position and check instrument placement for spine surgery interventions	XCY607-130099 2016 Sep 16 Revision: 6.0 Page 20 of 46
--	---	--

IGT systems Best Status: Final	Clinical Investigation Plan Observational clinical study with Surgical Navigation to plan, position and check instrument placement for spine surgery interventions	XCY607-130099 2016 Sep 16 Revision: 6.0 Page 21 of 46
--	---	--

IGT systems Best Status: Final	Clinical Investigation Plan Observational clinical study with Surgical Navigation to plan, position and check instrument placement for spine surgery interventions	XCY607-130099 2016 Sep 16 Revision: 6.0 Page 22 of 46
--	---	--

2.3. Conclusion of the justification for the design of the study

There is a clear need for accurate pedicle screw placement when stabilizing the spine to prevent damage to important structures. Image-guided navigation has shown to result in significantly accurate pedicle screw placement. With Surgical Navigation we have a similar image-guided technique as described in literature, but using real-time video overlay to align an instrument with a planned path.

The positive results of pre-clinical testing and a clinical study with Surgical Navigation has provided confidence to perform a clinical study related to pedicle screw placement in humans to further evaluate Surgical Navigation. An observational pilot study using Surgical Navigation in a small group of patients undergoing a spine surgery involving pedicle screw placement is the next step in evaluating Surgical Navigation in clinical use. An observational, non-comparative study design has been chosen based on the primary objective of the study (i.e., to estimate the overall proportion of screws accurately placed with the research procedure). The outcome of the study will provide for estimation of the mean accuracy and confidence intervals for Surgical Navigation system. These result will be compared with earlier found results in the pre-clinical testing and may be used to design future studies.

Alternative studies design were evaluated but not chosen for the following reasons:

- Based on previous literature studies with procedure where pedicle screws are placed, there is a large variability between the accuracy of placing pedicle screws (mostly 68%-94%, one study even reported 28% accuracy for the standard of care method (See table 1 in the Investigator Brochure). This is due to differences in pedicle width in the different areas in the spine (cervical/higher thoracic versus lumbar) and deformation of spine (especially with scoliotic patients). So there is an expected difference for the outcome for pedicle screw placement accuracy between different subjects and between different screws within a subject.
- Randomizing treatment groups, during procedure, within a patient (i.e., left versus right side) for a paired study design that control for the between subject variability is cumbersome and may affect the

IGT systems Best Status: Final	Clinical Investigation Plan Observational clinical study with Surgical Navigation to plan, position and check instrument placement for spine surgery interventions	XCY607-130099 2016 Sep 16 Revision: 6.0 Page 23 of 46
--	---	--

normal workflow for the procedure. Also, such step will increase the procedure time where patients are under sedation and lying with a large incision (increasing possible infections).

- Randomizing treatment groups to different subjects (i.e., standard of care and surgical navigation) may require extremely large study as the study will need to account for the variability within and between subjects. Also, the outcome of such comparison may not truly represent the therapy rather the patient condition.

2.4. Purpose of the study

The purpose of the study is to estimate the accuracy of the use of Surgical Navigation during spine procedures. Surgical Navigation is expected to provide assistance to the performing physician in aligning an instrument with a virtual path, planned on 3D image of the anatomy and overlaid on a live video image of the area of interest. Alignment of the instrument with the virtual planned path will potentially lead to placing the instrument at the desired location. Therefore the primary objective of the study is to estimate the accuracy of placement of pedicle screw with the assistance of Surgical Navigation. Secondary objectives will further assess other aspects of the use of Surgical Navigation in spine procedures, such as procedure time, usability (see APPENDIX III: USABILITY TESTING BACKGROUND) and workflow, patient dose and safety.

3. RISKS AND BENEFITS OF THE INVESTIGATIONAL DEVICE AND CLINICAL INVESTIGATION

The risk assessment process that Philips follows is in accordance with ISO 14971. This will ensure that the level of risk is assessed and risk mitigation measures (i.e. acceptable risk) are in place prior to start of the study.

[Redacted text]

Participation in the clinical study will provide no additional risk other than using the Surgical Navigation.

There are no possible interactions with concomitant medical treatments.

IGT systems Best Status: Final	Clinical Investigation Plan Observational clinical study with Surgical Navigation to plan, position and check instrument placement for spine surgery interventions	XCY607-130099 2016 Sep 16 Revision: 6.0 Page 24 of 46
--	---	--

A final risk assessment has been performed. The overall residual safety risk for the investigational device Surgical Navigation for the purpose of the clinical study is assessed to be acceptable. The investigational device Surgical Navigation is safe for clinical use based on the assessment of the individual risk profiles, the overall residual risks and supported by the earlier clinical study performed.

To facilitate safe and effective operation of the system by a trained healthcare professional, instructions for use are provided as part of the device labelling, as well as training at system handover.

The performed final safety assessment concluded that the potential benefits, as outlined above, clearly outweigh any potential risks associated with the use of this device in the clinical study.

Other documents which are related to the risk management activities (e.g. informed consent, Investigator Brochure, IFU) are in agreement with both the Risk Management File and the final conclusions given in the Risk Management Report

4. OBJECTIVES

4.1. Primary objective

The primary objective of this clinical investigation is to estimate the accuracy of pedicle screw placement using Surgical Navigation on post-procedural CBCT:

Screw placement will be evaluated using a slightly adapted Gertzbein⁴ classification for pedicle screw breach as follows:

grade 0 = breach 0 mm

grade 1 = lumbar and thoracic < 2 mm, cervical <1 mm breach distance

grade 2 = lumbar and thoracic 2-4 mm, cervical 1-2 mm breach distance

grade 3 = lumbar and thoracic > 4 mm, cervical >2 mm breach distance.

Accuracy will be reported by the proportion of pedicles having either grade 0 or 1.

4.2. Secondary objective(s)

The secondary objectives are:

- 1) To estimate the procedure time.
- 2) To estimate the average time to insert a pedicle screw.
- 3) To estimate the length of hospitalization (LOH)
- 4) Collect System Usability Scale (SUS) and assess the clinical workflow related to easiness to work, image quality, real-time image update, preparation of patient tracking, confidence in image guidance, access planning, 3D segmentation, motion compensation, identify unknown potential use errors and evaluate risk controls.
- 5) To estimate radiation dose (Dose Area Product (DAP) and Air Kerma (AK)) delivered to patient for:
 - a. Total procedure
 - b. During preparation and acquisition of CBCT for path planning
 - c. During screw/instrument placement (using fluoro).

IGT systems Best Status: Final	Clinical Investigation Plan Observational clinical study with Surgical Navigation to plan, position and check instrument placement for spine surgery interventions	XCY607-130099 2016 Sep 16 Revision: 6.0 Page 25 of 46
--	---	--

- d. During preparation and acquisition of CBCT for confirmation
- e. Average procedure dose per planned path
- 6) To estimate the total radiation dose (effective dose) received by operator, if DoseAware Xtend is available.
- 7) To describe procedure related complications
- 8) Report all adverse events
- 9) Report all adverse device effects
- 10) Report all device deficiencies that could have led to a serious adverse event

The objectives are descriptive in nature and are intended to provide additional information. There will be no pass or fail criteria.

5. STUDY DESIGN

5.1. General

This is a prospectively planned, single arm, single center study designed to estimate the accuracy of the pedicle screw placement using the Surgical Navigation procedure in patients undergoing pedicle screw fixation surgery. Accuracy will be reported by the proportion of pedicles having either grade 0 or 1 according to a slightly adapted Gertzbein⁴ classification. The slightly adapted Gertzbein⁴ classification for pedicle screw breach is defined as follows:

- grade 0 = breach 0 mm
- grade 1 = lumbar and thoracic < 2 mm, cervical <1 mm breach distance
- grade 2 = lumbar and thoracic 2-4 mm, cervical 1-2 mm breach distance
- grade 3 = lumbar and thoracic > 4 mm, cervical >2 mm breach distance.

The proportion of screws placed according to grade 0-3 will be estimated overall, and by region (e.g., cervical, lumbar, and thoracic). In addition, the number of lateral or medial perforations, the distance of the longitudinal axis of the screw and the planned path at the smallest diameter of the pedicle (mm), and the largest distance between screw tip and planned target of screw (mm) will be reported.

5.2. Investigational device exposure

Surgical Navigation is used for image-guided navigation during pedicle screw placements procedures for subjects participating in the study.

There are no additional devices or medications required for the study.

5.3. Subjects

5.3.1. In- and exclusion criteria

Subjects participating in the study will be carefully selected based on the next inclusion and exclusion criteria.

5.3.1.1. Inclusion criteria

- Subject will be undergoing a spine surgery with pedicle screw placement
- Subject is 16 years of age or older
- Subject is able to give informed consent

5.3.1.2. Exclusion criteria

- Subject participates in a potentially confounding device or drug trial during the course of the study.
- Subject meets an exclusion criteria according to national law (e.g. pregnant woman, breast feeding woman)

5.3.2. Enrollment and duration

Subjects are considered to be enrolled in the clinical investigation after they have signed the informed consent form. No study procedures will be performed before this moment.

IGT systems Best Status: Final	Clinical Investigation Plan Observational clinical study with Surgical Navigation to plan, position and check instrument placement for spine surgery interventions	XCY607-130099 2016 Sep 16 Revision: 6.0 Page 26 of 46
--	---	--

The subjects will be followed-up for this study until hospital discharge. After this the patient will be followed up according to standard of care outside the study.

The total duration of the study is expected to take approximately 1 year

5.3.3. Number of subjects

In total 240 screws placement are needed. It is expected that approximately 15 to 25 subjects with pedicle screw surgery are necessary to collect sufficient data for the evaluation of the primary and secondary objectives of this clinical investigation. After the first two subjects have been treated with pedicle screws there will be a delay of at least 1 week until the third and fourth subjects will be undergoing the procedure with Surgical Navigation. After subject one to four have been treated and the DMC/DSMB have been given recommendations of continuation of the study then there is no limit on how many subjects can be treated during one day. Enrollment of subjects will be stopped after approximately 240 screws are placed. This is a common number of screws used in studies showing accuracy of pedicle screw placement in the cervical²⁸. The enrollment period is expected to last for 7 months.

See section 6 Statistical considerations for more detail on the number of subjects.

5.3.4. Subject withdrawal or discontinuation

Subjects can withdraw informed consent at any time during the clinical investigation. There are no specific criteria for subject withdrawal or discontinuation.

5.4. Procedures

Pedicle screw placement

Pedicle screws will be placed using Surgical Navigation image guidance during spine surgery. The specific clinical investigation related steps for this spine surgery are (see also Figure 8):

- Sterile drapes compatible with the Allura and Surgical Navigation with transparent windows are placed over the detector.
- Several optical markers stickers (4-6 depending on the size of the region of interest) are placed at the back of the patient around the area of interest.
- A 3D CT like image is made (CBCT) of the relevant vertebrae.
- The spine image can be segmented using Surgical Navigation, if desired.
- The optimal path for the screw/instrument is planned in the CBCT volume.
- The optical view of Surgical Navigation is used to align the instrument (e.g. K-wires, screws instrumentation) with the planned path at the entry point. Progression view (view perpendicular to the planned path) using fluoro can be used during insertion of the screw, if desired. With this progression view function, the user can check on an x-ray image the actual placement of the screw at each moment in the procedure.
- The pedicle screws/instrumentation are further inserted in the vertebra using tools according to standard of care.
- Acquisition of a CBCT showing all placed pedicle screws/instrumentation to check the success of the procedure. This CBCT replaces the standard post-operative CT to check the procedure. For pedicle screw placement: Like in normal clinical practice, the necessity for revision of a pedicle screws is determined based on 3D information. This CBCT with the pedicle screws will be used to determine the accuracy of pedicle screw placement for the objectives of this study. The physician will indicate the classification according to the classification system (grade 0-3, see section 4.1). This classification can be done post-procedure.
- Time of the total procedure will be measured.
- Patient and occupational dose data will be collected using Surgical Navigation and DoseAware Xtend (if available at the hospital), respectively.

Patients participating in this study are subject to follow-up until hospital discharge to collect the length of hospital stay.

All other things are the same as the current standard of care.

IGT systems Best	Clinical Investigation Plan	XCY607-130099 2016 Sep 16 Revision: 6.0 Page 27 of 46
Status: Final	Observational clinical study with Surgical Navigation to plan, position and check instrument placement for spine surgery interventions	

All post-procedural CBCT acquisitions will be evaluated by an independent reviewer (neurosurgeon, orthopedic surgeon or spine surgeon experienced in pedicle screw placements) to determine the accuracy of pedicle screw placement according to the modified Gertzbein grading system (grade 0-3, see section 4.1) and direction (lateral/medial breach).

Furthermore, the distance (mm) between the following two points will be measured:

- The planned path and screw axis at smallest pedicle diameter
- The planned path and at the tip of the screw

The classification by the independent reviewer will be used for the objectives.

[figure not shown]

Figure 8: Flowchart for patient undergoing pedicle screw placement

Workflow feedback and usability information

Observations related to the workflow for the spine procedure will be performed by a Philips representative during some of the procedures. Workflow feedback will also be obtained through a short interview with the physician performing the procedure.

At the end of the study the physician(s) performing the procedure will be requested to complete a System Usability Scale (SUS) questionnaire to obtain general information related to the usability of Surgical Navigation related to these spine procedures.

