2. JUSTIFICATION FOR THE DESIGN OF THE STUDY

In spine surgery pedicle screws are used for fixation of the vertebrae to stabilize the vertebral column. Conditions where spinal fusion with pedicle screws may be considered include: degenerative disc disease, disc herniations, spinal deformity (scoliosis, kyphosis), spinal stenosis, sciatica, and radiculopathy, spine fractures and trauma, vertebral compression fracture, spine tumors, spondylolisthesis, spondylolysis, and spinal instability.

There is a clear need in spine surgery to place pedicle screws in the right place in the spine with good accuracy to avoid damage to important structures (spinal cord, nerve roots or vertebral arteries).

Thoracic levels (T3-T9) have the narrowest pedicles¹ and have decreased space between the medial border of the pedicle and spinal cord. Studies have estimated that screws placed in this region have a maximum permissible translational/rotational error tolerances ranged from 0.0 mm/0.0° at T5 to 3.8 mm/12.7° at L5 due

IGT systems Best Status: Final	Clinical Investigation Plan Observational clinical study with Surgical Navigation to plan, position and check instrument placement for spine surgery interventions	XCY607-130099 2016 Sep 16 Revision: 6.0 Page 15 of 46
--	---	--

to anatomically small pedicle diameters². Screw revision can be difficult and time-consuming (13.8±9.9 min), as the faulty screw track often hinders effective screw repositioning³. When considering screw revision time and possible decreases in biomechanical stability, it is important to place the pedicle screws correctly in the first attempt.

[figure not shown]

Figure 4: pedicle screw diameter

Image-guided spine surgery

The vast majority of pedicle screw placements in spine are performed using free-hand technique with or without use of 2D fluoro-guidance to place pedicle screws. Next to these conventional methods, image-guided navigation has become available as another technique to improve the accuracy of pedicle screw placement. Navigation systems are using different types of image data, i.e. either pre-operatively acquired CT images or intra-operatively acquired fluoroscopy images, intraoperative CBCT (e.g. O-arm (Medtronic)) or intra-operative acquired CT (e.g. AIRO iCT (Brainlab)). Intra-operative registration relies on the identification of anatomical landmarks, surface contours or pre-operatively implanted fiducial markers.

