6.5. Primary objective

Objective

The primary objective of this clinical investigation is to estimate the accuracy of pedicle screw placement using Surgical Navigation based on post-procedural CBCT:

Endpoint

The primary endpoint is the accuracy of screw placement. Screw placement will be evaluated using the slightly adapted Gertzbein⁴ classification for pedicle screw breach as follows:

- grade 0 = breach 0 mm
- grade 1 = lumbar and thoracic < 2 mm, cervical <1 mm breach distance
- grade 2 = lumbar and thoracic 2-4 mm, cervical 1-2 mm breach distance
- grade 3 = lumbar and thoracic > 4 mm, cervical >2 mm breach distance

Accuracy is defined as the proportion of screws with Gertzbein grade 0 or 1. The proportion of screws accurately placed will be estimated overall, and by region (e.g., cervical, lumbar, and thoracic).

In addition, the number of lateral or medial perforations, the distance of the longitudinal axis of the screw and the planned path at the smallest diameter of the pedicle (mm), and the largest distance between screw tip and planned target of screw (mm) will be reported.

See Appendix V: Background information primary objective for more information on the primary objective.

Analysis

The primary objective for this study is to estimate the overall proportion of screws accurately placed. All subjects who underwent treatment (ITT population) will be included in the primary efficacy analysis. Analysis will be performed assuming independence among different screws within a subject using Exact Clopper-Pearson 95% confidence interval. In addition, analysis will be performed using each subject as the unit for analysis. For this analysis, a two-sided 95% CI calculated for the accuracy of screw placement will be calculated using clustered binary data methodology as described by Zhou (2011)²⁹.

In addition, the proportion of screws accurately placed will be summarized by region (e.g., cervical, lumbar, and thoracic) and by grade 0-3. The 95% confidence interval will be presented.

IGT systems Best	Clinical Investigation Plan	XCY607-130099
Status: Final	Observational clinical study with Surgical Navigation to plan, position and check instrument placement for spine surgery interventions	2016 Sep 16 Revision: 6.0 Page 30 of 46

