16. DEFINITIONS AND ABBREVIATIONS

Abbreviations	Explanation of abbreviation
ADE	Adverse Device Effect
AE	Adverse Event
AK	Air Kerma
CBCT	Cone Beam Computed Tomography
CFR	Code Federal Regulations
CI	Confidence Interval
CRF	Case Report Form
DAP	Dose Area Product
DMC/DSMB	Data Monitoring Committee
e-CRF	Electronic Case Report Form
Entry point	The entry point is the point where the instrument (e.g. pedicle screws, screwdrivers, needle) will enter the body. The entry point can be the skin or the vertebrae, dependent on the type of procedure (Minimally invasive surgery or open surgery, respectively).
IFU	Instructions for Use
IM	Intramuscular
ISO	International Organization for Standardization
IV	Intravenous
MEC	Medical Ethic Committee
MDD	Medical Device Directive
OR	Odds Ratio
Placement	The actual position of the screw in the human body
SAE	Serious Adverse Event
SUS	System Usability Scale

IGT systems Best	Clinical Investigation Plan	XCY607-130099
Status: Final	Observational clinical study with Surgical Navigation to plan, position and check instrument placement for spine surgery interventions	2016 Sep 16 Revision: 6.0 Page 38 of 46

USADE	Unanticipated Serious Adverse Device Effect
-------	---

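### If a misplaced screw is revised, does the protocol leave open which CBCT grade counts in the primary endpoint?

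*Protocol*

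**What the plan says.** Section 5.4 describes a CBCT acquired when the screws are in, to check the result. In that step it says "the necessity for revision of a pedicle screws is determined based on 3D information" and then "This CBCT with the pedicle screws will be used to determine the accuracy of pedicle screw placement for the objectives of this study". The operating physician records a grade. Later in the same section, "All post-procedural CBCT acquisitions will be evaluated by an independent reviewer", and that reviewer's classification is the one used for the objectives.

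The endpoint is worded in two ways. Section 4.1: "Accuracy will be reported by the proportion of pedicles having either grade 0 or 1". Section 6.5: "Accuracy is defined as the proportion of screws with Gertzbein grade 0 or 1". Both base it on post-procedural CBCT and say nothing about revision.

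Two other places touch on the point. Section 16 defines placement as "The actual position of the screw in the human body". Section 2, on the time and stability cost of revising a screw, says "it is important to place the pedicle screws correctly in the first attempt".

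**The concern.** The scan that supplies the endpoint is also the scan on which revision is decided. A screw found in breach may therefore be moved, and if it is imaged again there are two grades for it. The sentence sending all post-procedural acquisitions to the independent reviewer has no selection rule, so it could be read as covering the repeat scan. The definition of placement as actual position carries no time point and could be taken to mean the final position. With pedicles as the unit in 4.1 and screws in 6.5, a screw replaced in the same pedicle might be one unit or two.

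What would be at stake is the meaning of the primary estimate. If the corrected grade replaced the first, a breach seen on the confirmation scan and then repaired would count as a success of the navigation system. That error can only raise the reported accuracy. Section 2.3 says the results will be compared with pre-clinical results and may inform later studies.

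**Working it through.** **Which image the text selects**

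1. Section 5.4 refers to the accuracy image in the singular, and it is the confirmation scan at which revision is judged.
2. The dose objectives (sections 4.2 and 6.6.5) divide CBCT use into two phases only, path planning and confirmation. Calling a scan post-procedural separates the confirmation scan from the planning scan.
3. With 15 to 25 subjects expected, all such acquisitions is the natural plural for one confirmation scan per subject. On that reading the two statements in 5.4 agree: one names the image, the other says every subject's image is read independently.
4. No visible passage prescribes a CBCT after revision. Without one there is no second grade to replace or duplicate the first. The flowchart, Figure 8, is not available, so it can neither confirm nor contradict this.
5. On the unit, section 6.5 defines accuracy in screws, and the sample size in 6.1 is 240 screws. Nothing suggests counting one position twice.

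**How large the effect could be on the other reading**

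Inputs from section 6.1: 240 screws, 85% assumed accuracy, target of a lower 95% limit above 77%, half-width about 5 points. Section 6.5 gives the Clopper-Pearson interval with screws treated as independent.

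The plan's figures first:
- Expected count: 0.85 × 240 = 204 accurate, 36 misplaced.
- Clopper-Pearson interval for 204/240: 79.8% to 89.3%. Half-width (89.3 − 79.8)/2 ≈ 4.7 points, in line with the stated 5.
- The lower limit first exceeds 77% at 198/240 (77.1%). Exact power at 85% is 87.9%, against the stated 80% or so. That difference is a separate matter and does not bear on this point.

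Let *f* be the fraction of the 36 misplaced screws that are revised and imaged again. The documents give no value, so *f* is assumed.

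| Counting rule | Formula | *f* = 0.10 | *f* = 0.25 | *f* = 0.50 |
|---|---|---|---|---|
| Confirmation-scan grade | 204/240 | 85.0% | 85.0% | 85.0% |
| Later grade replaces it, all corrected | (204 + 36*f*)/240 | 86.5% | 88.8% | 92.5% |
| Later grade replaces it, half corrected | (204 + 18*f*)/240 | 85.8% | 86.9% | 88.8% |
| Both grades counted, all corrected | (204 + 36*f*)/(240 + 36*f*) | 85.2% | 85.5% | 86.0% |

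Each screw whose corrected grade replaces a failing one adds 1/240 = 0.42 points. Twelve of them add 12/240 = 5 points, the planned half-width.

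Against the 77% target: at 204/240 the lower limit is already 79.8%, and replacement only raises it, so the target is met under either grade. To change the answer, first-scan accuracy must be lower. At an assumed 80% (192/240) the lower limit is 74.4% and the target is missed; correcting 12 of the 48 misplaced screws gives 204/240 and 79.8%, and it is met.

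**The case for a change.** The strongest case for a change is that which image defines a primary endpoint belongs in the protocol, and that sections 4.1, 5.4 and 6.5 set out to define it. The protocol foresees revision at the very step that generates the endpoint and gives no grading rule for a revised screw. A repeat scan is not prescribed, but it is not excluded either, and a literal reading of all acquisitions would take it in. The possible error runs one way and the remedy is a sentence.

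Part of this stands. If a screw is revised and imaged again, no visible sentence says expressly which grade enters the analysis, and the unit differs between 4.1 and 6.5. But that is a missing rule for an event the plan does not call for. How to treat an occasional repeat image can properly be settled in an analysis plan or in instructions for the image reader.

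The supporting passages do not carry it further. The definition of placement is silent on timing. The remark on first attempts is clinical background, and if it points anywhere it favours the confirmation scan. Nor would a written rule deliver a strict first-attempt accuracy: section 5.4 allows fluoroscopic checks throughout insertion, so a screw may be redirected before the confirmation scan is taken.

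**Conclusion.** No change to the plan follows. Applied as written, it gives one independent grade per screw from the confirmation scan, which is the method a stricter wording would prescribe. The remaining gap is an unwritten rule for an unprescribed repeat scan, and pedicles in 4.1 is loose wording where the analysis section and the sample size use screws.

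Any overstatement needs three things together: revisions after the confirmation scan, a further CBCT of those screws, and use of the later grade in place of the first. Under those assumptions the shift is 1.5 to 7.5 points when 10% to 50% of the 36 misplaced screws are corrected. It is at most 1.0 point over the same range if both grades are counted. At the planned 85% the 77% target is met either way, and the 80% case in which the conclusion would change is invented for illustration. That target is a sample-size planning aim; the study is a single-arm estimation study with no stated success test.

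This conclusion rests on reading the plural in 5.4 as one confirmation scan for each subject, and on the visible text, without the flowchart or an analysis plan.
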